4.6. Date Imputation

For the partial AE start dates, if month and day are missing, set to June 15. If day is missing, set to 15. If the imputed AE start date is after the AE end date, set AE start date to AE end date. If the AE start date is completely missing, no imputation will be done.

If the end of study date is missing, the last known visit date will be used. If the end of treatment date is partial (month and year is known), the last day of the month is used. If the end of treatment date is partial (only year is known) or is missing completely, the end of the study date is used.

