4.7.4. Safety analysis

SCD complications are defined as 'Yes' to the question 'is this a SCD Complication' in the SCD complications/AE form while the other AEs are defined as 'No' to the question 'is this a SCD Complication' in the SCD complications/AE form.

All safety analyses will be based on safety analysis set (Section 4.2). The analysis period for Pre-Oxbryta is 12 months before the first dose of Oxbryta and the analysis period for post-Oxbryta is from the first dose of Oxbryta through end of the study or the date of dose pausing or treatment discontinuation if the date of end of study date is missing.

SAEs and protocol-specified AEs will be classified according to the Medical Dictionary for Regulatory Activities (MedDRA). The frequency of SCD complications and other AEs treatment-emergent adverse events (TEAEs) and treatment emergent SAEs will be tabulated by system organ class, preferred term, severity (and total), and relationship to Oxbryta® (Voxelotor) treatment. The pregnancy outcomes and fertility will be reported as a listing. Any events (including deaths) leading to discontinuation of the study and SAEs will be listed.

A TEAE is defined as an AE that occurs during the effective duration of treatment defined as the time from the first dose of Oxbryta through end of treatment date or the end of study completion/discontinuation date (if the date of end of treatment is missing) +28 days.

On the AE case report form there is a question “Did AE start prior to first dose?”

- If the response is “Yes” or the adverse event start date is missing, and the end date is prior to the first dose of Oxbryta, then the AE is not considered a TEAE
- If the response is “No” or “Unknown”, then the AE is considered a TEAE

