4.7.5. Subgroup analyses

Analysis: The annualized incidence rate (per patient year) of rate of ‘Acute Pain Crisis’ (SCD Complications) will be performed by Pre-Oxbryta and Post-Oxbryta.

Analysis subgroups:

- Chronic pain
 - a. participants with chronic pain
 - b. participants without chronic pain
- Maximum increase from Pre-Oxbryta in Hb
 - a. Full analysis set for participants with > 1 g/dL maximum increase from Pre-Oxbryta in Hb
 - b. Full analysis set for participants with <= 1 g/dL maximum increase from Pre-Oxbryta in Hb

Analysis: Annualized incidence VOC rate for pre-Oxbryta and post-Oxbryta will be reported.

The VOC event for Pre-Oxbryta is defined as 1) SCD complication with ‘Acute Pain Crisis’ in the Pre-Oxbryta SCD complication page or 2) any qualifying complications from SCD AE prior to Treatment Start Date.

The VOC event for Post-Oxbryta is defined as any qualifying complications from SCD AE on or after the treatment start date.

The qualifying complications from SCD AE are those that met at least one of the following two conditions:

- AE preferred term (AEDECOD) to be 'Sickle cell anaemia crisis';
- type of complications (CMPTYP) is 'Acute Pain Crisis'

- 1) Analysis population: Safety analysis set where participants had a non-missing Pre-Oxbryta SCD complications will be included in the analysis.
- 2) Analysis population: Safety analysis set where participants who had a non-missing Pre-Oxbryta SCD complications or participants who had an adverse events reported in Pre-Oxbryta or Post-Oxbryta will be included in the analysis.

Analysis: The annualized VOC incidence rate (per patient year) will be performed by Pre-Oxbryta and Post-Oxbryta.

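### Partial AE start dates are imputed without reference to first dose, so some AE-form crises can be counted in the wrong pre/post period, against the CRF's own answer

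*SAP*

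**What the plan says.** SAP 4.6 has four rules for AE start dates:

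- Month and day missing: "For the partial AE start dates, if month and day are missing, set to June 15".
- Day missing: "If day is missing, set to 15".
- Cap: "If the imputed AE start date is after the AE end date, set AE start date to AE end date".
- Nothing known: "If the AE start date is completely missing, no imputation will be done".

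First dose appears in none of them.

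SAP 4.7.5 defines a pre-Oxbryta VOC by two routes. The first is by CRF page: "SCD complication with ‘Acute Pain Crisis’ in the Pre-Oxbryta SCD complication page". The second is by date: "any qualifying complications from SCD AE prior to Treatment Start Date". A post-Oxbryta VOC has only the date route: "any qualifying complications from SCD AE on or after the treatment start date".

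SAP 4.7.4 reports that the AE form asks whether the event started before first dose. For 'No' or 'Unknown', "then the AE is considered a TEAE". The event is not treatment-emergent if the answer is 'Yes', or the start date is missing, and the end date is before first dose. Neither SAP 4.6 nor the VOC definition in SAP 4.7.5 uses that answer, and no section says which source prevails when the imputed date and the answer disagree.

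**The concern.** Two rules decide, for the same event, whether it belongs before or after treatment, and they can disagree. The site has recorded which side of first dose the event fell on, yet the VOC count can overrule it with an arbitrary calendar date. The annualized crisis rate before and after first dose is one of the few effectiveness comparisons left in the abbreviated report. A crisis moved from post to pre raises one rate and lowers the other; a move from pre to post does the reverse. The same crisis could also appear as treatment-emergent in the safety tables and as a pre-treatment event in the rate tables.

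**Working it through.** The plan states no figure to reproduce: it gives neither a count of partial dates nor a count of crises. The check applies the SAP 4.6 rule directly.

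**Who can be misplaced.** The imputed date stays in the known month or year unless the cap moves it to the recorded end date. An AE-form event can therefore change sides only if its known month (day missing) or known year (month and day missing) contains first dose. Crises on the Pre-Oxbryta complication page count as pre whatever the AE-form date.

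**Two worked cases.**

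1. First dose 20 June, onset 24 June, day missing, answer 'No'. The imputed date is 15 June. SAP 4.7.5 counts a pre-Oxbryta VOC; SAP 4.7.4 counts a treatment-emergent event.
2. First dose 1 March, onset in February, only the year known, answer 'Yes'. With no end date, the imputed date is 15 June and the crisis counts as post. With a February end date, the cap pulls the start back to February and it stays pre.

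**Role of the cap.** It can only move a start date earlier. It therefore blocks some pre-to-post moves, namely those with an end date before first dose, and no post-to-pre moves.

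**Conditional size.** Assume onset is uniform over the known period and ignore the cap.

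Year-only dates, 365-day year, first dose on day d; 15 June is day 166:

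- d ≤ 166: the imputed date is on or after first dose, and the share misplaced (pre to post) is (d − 1)/365.
- d > 166: the imputed date is before first dose, and the share misplaced (post to pre) is (366 − d)/365.

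| First dose | Day d | Share misplaced | Direction |
|---|---|---|---|
| 1 March | 60 | 59/365 = 16% | pre to post |
| 15 March | 74 | 73/365 = 20% | pre to post |
| 15 June | 166 | 165/365 = 45% | pre to post |
| 16 June | 167 | 199/365 = 55% | post to pre |
| 15 September | 258 | 108/365 = 30% | post to pre |
| 1 October | 274 | 92/365 = 25% | post to pre |

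Averaged over all 365 first-dose days:

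- pre to post: (0 + 1 + … + 165)/365² = 13,695/133,225 = 10.3%
- post to pre: (1 + 2 + … + 199)/365² = 19,900/133,225 = 14.9%
- total: 25.2%

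Day-missing dates, 30-day month, first dose on day d: (d − 1)/30 pre to post if d ≤ 15, and (31 − d)/30 post to pre if d > 15. Averages over the month:

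- pre to post: 105/900 = 11.7%
- post to pre: 120/900 = 13.3%
- total: 225/900 = 25%

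Under uniform onset, restoring the cap can only lower the pre-to-post figures, so the totals are upper bounds. Another onset pattern could shift them either way.

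**The case against.** The strongest reply is that few crises can be affected and the plan already has two safeguards. The cap keeps a year-only crisis pre if it ended before first dose. The complication-page route fixes pre-treatment crises by page, and Protocol 10.3.6.1.2 has all complications of the 12 months before treatment recorded in the CRF. A VOC, by Protocol 10.3.6.1.3, involves a facility visit or contact with a provider, so a year-only date may be rare. The exposed tables are descriptive, Appendix A labels them as subgroup or ad hoc, and no sample size calculation rests on them.

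All of that stands, and it limits reach and size. It does not remove the conflict. The cap gives no protection in the first worked case, and the complication page does not help a post-treatment crisis, whose only route is by date.

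Three stronger readings are tempting, and the documents do not support them:

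- *All year-only events in the first-dose year fall on one side.* For AE-form events this is so when first dose is after 15 June. When it is on or before 15 June, events with an end date before first dose stay pre.
- *The rule flatters the drug.* Post-to-pre moves would do so, but first doses up to the 15th or 15 June produce moves the other way. The net direction depends on first-dose dates, which are not given.
- *The safety tables are wrong too.* Treatment-emergent status follows mainly the CRF answer, so those tables are largely untouched.

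**Conclusion.** The plan is wrong as written on a narrow point. For an AE-form crisis with a partial start date compatible with the first-dose month or year, SAP 4.6 and 4.7.5 together can assign the wrong period, although the CRF holds the answer that would prevent it. A 'No' can become a pre-Oxbryta VOC. A 'Yes' can become a post-Oxbryta VOC if the end date is missing or is on or after first dose. The outputs at risk are the pre/post crisis rates of SAP 4.7.5, Tables 15.5.1 to 15.5.5.

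Up to about a quarter of such events would be misplaced on average, given uniform onset and no cap. That is a share of an unknown and possibly very small number, so it says nothing about the error in the rates themselves, which is likely small. The conclusion also takes the date used in SAP 4.7.5 to be the start date as imputed under SAP 4.6; SAP 4.7.5 names no date variable, and no other rule supplies one.

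**What to change.** Add to SAP 4.6, for a partial start date compatible with the month or year of first dose:

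- 'No': use the later of the imputed date and first dose.
- 'Yes': use the earlier of the imputed date and the day before first dose.
- 'Unknown': use first dose as the lower bound only if the end date is missing or is on or after first dose; otherwise the event is pre.
- Apply the end-date cap last, and query any 'No' whose end date is before first dose.

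In SAP 4.7.5, state that the VOC period is assigned from the resulting date. Where the start date is completely missing, which SAP 4.6 leaves unimputed and SAP 4.7.5 cannot place, assign it from the CRF answer.

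In the first worked case the date becomes 20 June and the crisis is post, in line with its treatment-emergent status. In the second it becomes the day before 1 March and the crisis is pre. The end-date condition on 'Unknown' matters: with first dose 20 June, day missing and end date 10 June, an unconditional lower bound would put the start after the end and count a crisis that was over before treatment as post.

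The cost is a few sentences and one derivation, using fields already collected. Reporting the number of partial-date crises in the first-dose month or year would show whether the point matters for the rates.

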10.4.1.2. Early Discontinuation of Oxbryta® (Voxelotol)

Participants may be discontinued from Oxbryta® (Voxelotol) treatment by the study doctor or treating physician at any time and for any reason.

Participants who are discontinued or withdraw from Oxbryta® (Voxelotol) treatment will continue to be followed for up to 5 years after the first dose of Oxbryta® (Voxelotol) treatment unless they withdraw consent for study participation.

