4. RESEARCH METHODS

4.1. Study design

This registry is an observational study designed to evaluate the effect of Oxbryta® (Voxelotor) in individuals with SCD. This registry is intended to benefit and support interests of participants, clinicians, regulatory bodies, payers, and industry by obtaining longitudinal data on Oxbryta® (Voxelotor). Approximately 500 participants with SCD who are prescribed and treated with Oxbryta® (Voxelotor) will be enrolled. The study will be conducted at approximately 35 sites in the US.

Any participant who is currently taking Oxbryta® (Voxelotor) or has been prescribed and will initiate treatment with Oxbryta® (Voxelotor), is eligible to participate. Eligible participants will receive treatment with Oxbryta® (Voxelotor) as prescribed by their physicians, as part of their usual care. Participants will be treated and evaluated per standard of care (SOC) and at the physician's discretion.

Participants will be introduced to the study by their health care team and will sign the informed consent form (ICF) or assent prior to any data collection for the study.

[figure not shown]
This study will collect data that are recorded in the participants' medical records and other secondary data sources such as Insurance and Pharmacy Claims. Study data will be collected at regular intervals (no more frequent than every 3 months) and entered in case report forms (CRFs) via an electronic data capture (EDC) system by the study staff.

Regardless of how long participants have been on Oxbryta® (Voxelotor) when they enroll in the study, participants will be followed for up to 5 years after their first dose of Oxbryta® (Voxelotor) treatment, or until they withdraw their consent to participate, or are discontinued from the study. Treatment, including interruptions and restarting treatment, will continue at the discretion of the treating physician, and there are no pre-defined treatment requirements. Participants may receive any additional medications prescribed by their treating physician or have any medical interventions that are deemed appropriate by the treating physician or study doctor. The participant or treating physician may discontinue Oxbryta® (Voxelotor) at any time. Participants who discontinue treatment with Oxbryta® (Voxelotor) earlier than 5 years will continue to be followed on study to collect clinical and health-related quality of life (HRQoL) outcomes for up to 5 years after their first dose of Oxbryta® (Voxelotor) treatment.

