4.7.1. Index date and follow-up

The index date is defined as the inform consent date. The Post Oxbryta period is from the first dose of Oxbryta to the date of end of treatment or end of study.

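### SAP 4.6 replaces a year-only end-of-treatment date with the end-of-study date, which can place the stop years after the recorded year

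*SAP*

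**What the plan says.** SAP Section 4.6 has one rule for two situations: "If the end of treatment date is partial (only year is known) or is missing completely, the end of the study date is used". A stop date with a known year is therefore handled as if nothing were known, with no cap at the end of that year.

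The neighbouring rules in the same section keep what is known:

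- End of treatment with month and year: "If the end of treatment date is partial (month and year is known), the last day of the month is used".
- Adverse event start with year only: "if month and day are missing, set to June 15".
- End of study: "If the end of study date is missing, the last known visit date will be used".

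End of study is not close to end of treatment by design. SAP Section 4.1 says "Participants who discontinue treatment with Oxbryta® (Voxelotor) earlier than 5 years will continue to be followed on study", and Protocol Section 10.4.1.2 says that those who stop "will continue to be followed for up to 5 years after the first dose".

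The end-of-treatment date is named in two later places. SAP Section 4.7.1 says "The Post Oxbryta period is from the first dose of Oxbryta to the date of end of treatment or end of study", and Section 4.7 builds patient-years from that duration. SAP Section 4.7.4 ends the window for treatment-emergent adverse events (TEAEs) 28 days after end of treatment, or after end of study if the treatment date is missing.

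**The concern.** A stop recorded as 2022 cannot have happened in 2025 or 2027, yet the rule assigns such a date whenever follow-up continues past the recorded year. The imputed value then contradicts the data it is meant to complete. It also departs from the approach that Section 4.6 takes to the other partial dates.

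Three outputs could carry off-drug time as if it were treated time: the drug-administration duration categories (Section 4.7.3, Table 15.1.4), the TEAE window (Section 4.7.4), and the patient-years behind the annualized rates (Sections 4.7 and 4.7.1). The documents support these effects to different degrees.

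**Working it through.** The plan states no exposure total and no number of partial dates, so there is no figure to reproduce. The check is date arithmetic.

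**Inputs from the documents.** The Section 4.6 rules above; follow-up of at most 5 years from first dose (SAP 4.1); start of data collection 2 February 2022 (Protocol Section 6); date of SAP version 3, 24 January 2025 (version history); duration categories from under 1 month to 48 months or more (SAP 4.7.3).

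**Assumed.** All individual dates below, chosen within those limits.

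**Formulas.** F = first dose, S = end of study, Y = 31 December of the recorded stop year; years = days / 365.25.

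- Duration under the SAP rule = S − F
- Longest duration the record allows = min(Y, S) − F
- Time ruled out by the record = S − min(Y, S)

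| Case | F | Recorded year | S | SAP rule | Record allows at most | Ruled out |
|---|---|---|---|---|---|---|
| 1 | 2 Feb 2022 | 2022 | 2 Feb 2027 | 1826 d = 5.00 y | 332 d = 0.91 y | 1494 d = 4.09 y |
| 2 | 2 Feb 2022 | 2022 | 24 Jan 2025 | 1087 d = 2.98 y | 332 d = 0.91 y | 755 d = 2.07 y |
| 3 | 1 Jul 2022 | 2024 | 1 Jul 2027 | 1826 d = 5.00 y | 914 d = 2.50 y | 912 d = 2.50 y |
| 4 | 1 Dec 2022 | 2022 | 1 Dec 2027 | 1826 d = 5.00 y | 30 d = 0.08 y | 1796 d = 4.92 y |
| 5 | 10 Jan 2023 | 2024 | 1 Sep 2024 | 600 d = 1.64 y | 600 d = 1.64 y | 0 |

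Case 4 is close to the upper bound of 5 years. Case 5 shows that the rule does no provable harm when the study ends in the recorded year.

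**One true stop date.** In case 1, suppose the true stop was 15 March 2022. True exposure is 41 d = 0.11 y, in the category from 1 to under 2 months. If duration runs to the imputed date, the SAP rule gives 5.00 y, in the category of 48 months or more; the error is 1785 d = 4.89 y. A cap at 31 December 2022 gives 0.91 y, an error of 291 d = 0.80 y. Under the cap the error is always below 1 year, because the true and imputed dates lie in the same calendar year.

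**Effect on a rate, only if patient-years end at end of treatment.** Let T be mean true on-treatment years, q the share of participants with year-only dates and x their mean excess years. If no further events are counted, the rate is multiplied by T / (T + qx). With T of 1 to 2 and x of 1 to 4 (all assumed):

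- q = 1%: 2/(2 + 0.01) = 0.995 to 1/(1 + 0.04) = 0.962
- q = 5%: 2/(2 + 0.05) = 0.976 to 1/(1 + 0.20) = 0.833
- q = 10%: 2/(2 + 0.10) = 0.952 to 1/(1 + 0.40) = 0.714

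If events in the added time are counted as well, with on-drug rate r and off-drug rate s, the result is (rT + sqx) / (T + qx). This weighted average of r and s is below r if s is lower and above r if s is higher, so the direction is not fixed.

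**The case against.** The case against making much of this is strong on consequences.

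- **Rates.** A reader might infer that annualized rates are diluted. Section 4.7.1 names both end dates without saying which governs. Section 4.7.4 runs the safety post-Oxbryta period to end of study and falls back on dose pausing or discontinuation only when that date is missing. If end of study governs, this imputation changes no denominator. If end of treatment governs, added events may offset or reverse the dilution.
- **TEAEs.** A reader might infer that this rule is what labels late off-drug events as treatment-emergent. The window is stretched, but the case report form rule in Section 4.7.4 counts any event answered No or Unknown to starting before first dose, with no test against an end date. Under that rule such events count even with an exact stop date.
- **Exposure.** No formula for duration is given. The exposure variable comes from the physician administration form, while end of treatment has its own form (SAP 4.3). The effect on Table 15.1.4 is likely but inferred.
- **Size.** Case 1 is near the worst case, the number of year-only dates is unknown, and the report is abbreviated and descriptive. The date of SAP version 3 may point to shorter follow-up than 5 years, although the Protocol milestones still run to 2030.
- **Completely missing dates.** A reader might extend the criticism to these. No recorded year is contradicted there, and end of study suits a participant still on treatment. The documents show no error in that part of the rule.

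All of this stands as a limit on impact. None of it defends assigning a date that the recorded year excludes.

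**Conclusion.** Wrong as written, minor severity. The reading of the rule is certain: a known year is discarded, against the handling of the other partial dates in Section 4.6. For one participant the time ruled out by the record ranges from zero to just under 5 years; it is about 4.1 years in case 1 and about 2.1 years if the study ended on 24 January 2025. These figures rest on assumed dates.

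Exposure duration is affected if it runs to the imputed date. Patient-years are affected only if Section 4.7.1 means end of treatment, and the bias in the rates then has no fixed direction. TEAE counts may change little. The aggregate effect is unknown because the frequency of year-only dates is not stated; the 1% to 10% range above is illustrative.

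**What to change.** In SAP Section 4.6, separate the year-only case from the completely missing case: if only the year of end of treatment is known, use the earlier of 31 December of that year and the end-of-study date. This extends the section's own last-day-of-month rule to the year and keeps the error below 1 year.

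The cost is one sentence in the SAP and the matching line in the date derivation. No new data are needed, and the rule for completely missing dates can stay. The change does not settle which end date Section 4.7.1 intends; that is a separate point.

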4.7. Statistical methodology and analyses

The following general analysis will be followed for this study, unless otherwise specified.

Unless otherwise specified, continuous/quantitative variables will be summarized using descriptive statistics which will include the number of participants with data to be summarized (n), mean, standard deviation (SD), median, first and third quartile (Q1, Q3), minimum, maximum, and the number of missing observations. Minimum and maximum will be reported with the same number of decimal places as collected in raw data, while mean, median, Q1, Q3 will be reported with one extra decimal place, and SD will be reported with two extra decimal places. Descriptive statistics for categorical/qualitative variables will be presented with number of participants and percentage (%) of participants in each category.

Percentages will not include the missing category and will be calculated over the number of participants with available (non-missing) data. A category with a zero count will be presented as “0” and a category with a 100 percentage will be displayed as “100”.

The annualized incidence rate is defined as total numbers of a given event for all participants divided by the total patient-year where the total patient-year is defined as the sum of total duration (years) as defined in the Section 4.7.1 for all participants.

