9.11.3. Effectiveness Endpoint Measures Analyses

Baseline Demographic Characteristics:

Baseline demographic characteristics will be summarized descriptively.

Endpoints:

- Change from pre-Oxbryta® (Voxelotor) treatment period in Hb, hemolysis measures, measures of iron overload, and renal function over time will be summarized descriptively.
- Annualized rate of significant SCD-related clinical events, for example VOC, ACS, priapism, stroke, TIA, chronic or end stage kidney disease, iron overload, leg ulcers, cardiac malfunction, and PH will be calculated. The association between change in Hbhemolysis marker and rates of SCD-related clinical events will be evaluated.
- Rates of outpatient visits (including infusion center, acute care, or telemedicine visit), ED visits, hospitalizations, acute and chronic RBC transfusions, home oxygen supplementation, and renal dialysis will be summarized with a similar approach as incidences of SCD-related clinical events. The total cost associated with clinical interventions will be summarized descriptively.

- HRQoL measures over time will be summarized descriptively. Proportions of participants with improved HRQoL measures will be calculated and the associated 95% Clopper Pearson Exact confidence intervals will be constructed as appropriate.
- Rates of SCD-related clinical events, healthcare resource utilization, total cost associated with clinical interventions (if available) and HRQoL while on Oxbryta® (Voxelotor) treatment will be compared with the corresponding measures prior to the first dose of Oxbryta® (Voxelotor) treatment, as appropriate.

Subgroup analysis:

Similar comparisons may be performed between the subgroup of participants who discontinue Oxbryta® (Voxelotor) treatment but remain in the study and those participants who remain on Oxbryta® (Voxelotor).

Other subgroup or sensitivity analyses may be performed.

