10.3.3. Medical History, Demographic Data, and Insurance Information

Medical history will be recorded for up to 12 months prior to the first dose of Oxbryta® (Voxelotor) (retrospective data). Medical history will include all available SCD genotype results and significant medical history, including hematological parameters.

Demographics (sex, race, ethnicity, and age) and SCD characteristics will be recorded at pre-Oxbryta® (Voxelotor) treatment period, using the most recent data before enrollment.

Information on the participant's insurance payer will also be collected (eg, Medicaid, Medicare, dual eligible, private, or self-insured).

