4.3. Variables

Variable	Role	Data source(s)	Operational definition
Index date	Study period	Case report form	Inform consent date
Index year	Study period	Case report form	Inform consent date
Pre-Oxbryta	Study period	Case report form	Baseline: any assessments within 12 months before receiving first dose of Oxbryta® (Voxelotor)
Post-Oxbryta	Study period	Case report form	Follow-up period for up to 5 years after the first dose of Oxbryta® (Voxelotor)
End of Treatment	Study period	Case report form	Captured from end of treatment form
End of Study	Study period	Case report form	Captured from end of study form
Age	Demographics	Case report form	Age at first dose of Oxbryta
Sex	Demographics	Case report form	Captured from the inform consent and eligibility form
Race/Ethnicity	Demographics	Case report form	Captured from the inform consent and eligibility form

SCD genotype	SCD disease history	Case report form	Captured from SCD disease history form
Hydroxyurea use	SCD disease history	Case report form	Captured from SCD disease history form
Height	Baseline characteristics	Case report form	Captured from Physical examination form
Weight	Baseline characteristics	Case report form	Captured from Physical examination form
Pre-Oxbryta SCD complications	Medical history	Case report form	Captured from Pre-Oxbryta treatment form
Concomitant Medications	Concomitant Medications	Case report form	Captured from concomitant medications form
Hemoglobin	Effectiveness endpoint measures - Hematology	Case report form	Captured from laboratory assessment-Hematology form
Reticulocyte count (%)	Effectiveness endpoint measures - Hematology	Case report form	Captured from laboratory assessment-Hematology form
Reticulocyte count (absolute)	Effectiveness endpoint measures - Hematology	Case report form	Captured from laboratory assessment-Hematology form
White blood cells (WBC)	Effectiveness endpoint measures - Hematology	Case report form	Captured from laboratory assessment-Hematology form
Aspartate Aminotransferase (AST)	Effectiveness endpoint measures - Hematology	Case report form	Captured from laboratory assessment-Hematology form
Alanine Aminotransferase (ALT)	Effectiveness endpoint measures - Hematology	Case report form	Captured from laboratory assessment-Hematology form
Bilirubin (Total)	Effectiveness endpoint measures - Chemistry	Case report form	Captured from laboratory assessment-Chemistry form

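### The pooled crisis rate weights participants about equally before first dose but by follow-up time after it, so the pre/post contrast can shift in either direction with no drug effect, and it carries no interval

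*SAP*

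**What the plan says.** SAP 4.7 defines a single pooled rate: "The annualized incidence rate is defined as total numbers of a given event for all participants divided by the total patient-year". For the denominator, "the total patient-year is defined as the sum of total duration (years) as defined in the Section 4.7.1 for all participants".

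SAP 4.7.1 gives only one duration: "The Post Oxbryta period is from the first dose of Oxbryta to the date of end of treatment or end of study". It gives none for the pre period. That comes from the safety section, SAP 4.7.4: "The analysis period for Pre-Oxbryta is 12 months before the first dose of Oxbryta". Protocol 10.3.3, however, says medical history is recorded for up to 12 months, so some histories may be shorter. SAP 4.3 caps the post period at 5 years after first dose.

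SAP 4.7.5 uses the pooled rate for both periods: "The annualized VOC incidence rate (per patient year) will be performed by Pre-Oxbryta and Post-Oxbryta". It does the same for acute pain crisis in the chronic-pain and maximum-Hb-increase subgroups. Tables 15.5.1 to 15.5.5 report these rates.

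Protocol 9.11.3 says on-treatment rates "will be compared with the corresponding measures prior to the first dose", with the qualifier that this is done as appropriate. Neither document names a method for that comparison. The only interval in either document is the Clopper-Pearson interval for HRQoL proportions in the protocol.

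**The concern.** Two rates placed side by side invite a ratio, and the ratio is interpretable only if both rates describe the same mix of participants. Here they need not. With one year each before first dose, every participant has the same weight in the pre rate. After first dose, someone followed for 4 years has eight times the weight of someone followed for 6 months. If frequent-crisis participants have shorter follow-up, the post rate falls through weighting alone; if they have longer follow-up, it rises.

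Without an interval, a reader also cannot tell a weighting artefact or chance variation from an effect. The SAP says its limited efficacy data are to support the benefit-risk evaluation, and PROMIS has been dropped from the planned report, so these crisis rates are likely to be read as evidence of clinical effect.

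**Working it through.** The plan gives no crisis rate, dispersion or expected follow-up, so there is no figure to reproduce. All rates and durations below are assumptions; the formula is the SAP's.

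**Formula.** Let participant *i* have a constant crisis rate λᵢ, the same before and after first dose (no drug effect), 1 year of pre time and Tᵢ years of post time.

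- Pre rate = mean(λ)
- Post rate = Σ λᵢTᵢ / Σ Tᵢ
- Post/pre ratio = 1 + cov(λ, T) / [mean(λ) × mean(T)]

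The ratio is 1 only if rate and follow-up are uncorrelated, and the sign of the bias is the sign of the covariance.

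**Two equal-sized groups, true ratio 1:**

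| Rates per year | Post years | Pre rate | Post rate | Ratio |
|---|---|---|---|---|
| 4 and 1 | 1 and 3 | 2.5 | (4×1 + 1×3)/4 = 1.75 | 0.70 |
| 3 and 2 | 1 and 3 | 2.5 | (3×1 + 2×3)/4 = 2.25 | 0.90 |
| 4 and 2 | 4 and 1 | 3.0 | (4×4 + 2×1)/5 = 3.60 | 1.20 |
| 4 and 2 | 2.5 and 2.5 | 3.0 | (4×2.5 + 2×2.5)/5 = 3.00 | 1.00 |
| 4 and 1 (extreme) | 0.5 and 4 | 2.5 | (4×0.5 + 1×4)/4.5 = 1.33 | 0.53 |

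**Simulation.** 500 participants, mean 3 events per year, gamma-distributed rates (shape 1 / shape 2), and exponential exposure scaled by (rate/mean)^(−b) and bounded to 1 month–5 years. The mean pooled ratio was 1.00/1.00 at b = 0, 0.87/0.93 at b = 0.25, 0.77/0.86 at b = 0.5, 0.64/0.77 at b = 1, and 1.30/1.16 at b = −0.5 (high-rate participants followed longer).

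**Does a within-participant ratio remove it?** The conditional Poisson estimate *r* solves Σ y₁ = Σ (y₀ + y₁) rT/(1 + rT). Putting in expected counts y₀ = λ and y₁ = λT at r = 1, each term on the right is (λ + λT)·T/(1 + T) = λT, which equals y₁ whatever the pairing of λ and T. In the simulations it averaged 0.998 to 1.002.

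**Does a random-effect model remove it?** A Poisson model with a gamma participant effect, log person-time offset and period term gave about 0.79 (4 and 1; 0.5 and 4 years), 0.91 (4 and 1; 1 and 3 years) and 0.91 to 0.92 (3 and 2; 1 and 3 years). It assumes that the rate is independent of follow-up, which is the condition in doubt.

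**Interval.** In the simulations the relative standard error of the post rate was 1.6–1.9% under a plain Poisson model and 4.0–5.7% with participant clustering. For the post/pre ratio the gap is smaller, because a participant's own level partly cancels: with exposure unrelated to rate, the empirical standard error of the log ratio was 1.26 times the Poisson value at gamma shape 2 and 1.48 times at shape 1.

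**The case against.** The SAP is descriptive. It has no formal sample size calculation, names no test or ratio, and calls its efficacy data limited. The pre/post crisis rates sit under subgroup analyses, in tables labelled subgroup or ad-hoc, while the main complication-rate analysis in SAP 4.7.3 covers the treatment period without a pre comparator. Protocol 9.13 already admits susceptibility to bias when outcomes are compared. All of this stands, and it limits the importance of the point. It does not remove it, because the two rates are still reported together and the protocol anticipates comparing them.

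Four stronger readings are tempting and are not supported:

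- *That the contrast is biased in the drug's favour.* The documents give no information on whether frequent-crisis participants have shorter or longer follow-up, so neither the direction nor the size is known.
- *That it is the trial's main clinical-effect result.* The plan does not designate it so.
- *That persistence on drug sets the weights.* SAP 4.7.1 ends post time at end of treatment or end of study. SAP 4.7.4 runs it through end of study, using pausing or discontinuation only if that date is missing, and participants who stop the drug remain in follow-up. Under the second statement, study follow-up sets the weights. Post time varies by person under either.
- *That the planned interval is two to three times too narrow.* The SAP plans no interval. An inflation factor for a single pooled rate also overstates the problem for a pre/post ratio.

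**Conclusion.** The point holds as a conditional one. As written, the pre and post rates weight participants differently, and the contrast departs from 1 with no drug effect whenever follow-up is associated with underlying crisis rate. With moderate assumed differences the ratio ranges from 0.70 to 1.20; without the association it is 1.00. This rests on one year of pre time being assigned to each participant, which SAP 4.7.4 implies but SAP 4.7.1 does not state, and on post time differing between participants, which both documents allow. The absence of any interval for event rates is a plain gap. Given the descriptive status of these tables, this should be fixed and is a cheap improvement; it does not invalidate the plan.

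**What to change.** 1. In SAP 4.7.1, define the pre-period duration for each participant from the months of history actually available. Reconcile the end of the post period between SAP 4.7.1 and SAP 4.7.4, and count events and person-time over the same window.
2. In each pre/post crisis or VOC table (15.5.1 to 15.5.5), keep the pooled rates as description. Add a within-participant post/pre rate ratio from a conditional (participant fixed-effect) Poisson model with a log person-time offset, and a 95% interval from participant-level robust or bootstrap variance. Do not substitute a participant random-effect model.
3. State the limits beside the ratio. Participants with no events in either period do not contribute. The model corrects the weighting only: it does not correct regression to the mean or stopping triggered by a recent crisis. In a further check with a true ratio of 1 and an assumed 5–30% chance of stopping after each crisis, the conditional ratio drifted to 1.04–1.17.

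The cost is one extra model per table and a few lines of SAP text. No new data are needed.
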